9.4.2. Secondary Efficacy Endpoints in the Apremilast Extension Phase

The analyses will be conducted using the ITT population for subjects who entered the Apremilast Extension Phase. For binary endpoints, frequency tables will be provided by time point based on data with NRI. For continuous endpoints, summary statistics will be provided by time point (including end of phase assessment) on DAO.

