9.2. Study Population Definitions

Four analysis populations will be defined for this study. These populations include the safety population, the intent to treat (ITT) population, the per protocol (PP) population, and the apremilast exposure population.

- The Safety population will consist of all subjects who are randomized and receive at least one dose of investigational product (IP). This set of subjects will be included in the treatment group corresponding to the IP they actually receive. This will be the population for all safety analyses on data from the Placebo-controlled Phase.
- The ITT population will consist of all subjects who are randomized. This will be the primary population for the primary endpoint and all other quality of life and efficacy analyses. Baseline summaries will also be based on the ITT population.
- The PP population will consist of all subjects who are in the ITT population, complete the Placebo-controlled Phase, and have no major protocol violations. The PP population will only be used to supplement the primary endpoint ITT analysis.
- The apremilast (APR) exposure population will consist of only those subjects who receive at least one dose of apremilast treatment. The APR exposure population will only be used for the purposes of safety reporting including all safety data during apremilast treatment.

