4.4. Sample Size Determination

For the primary endpoint, i.e., the response rate (π) defined as the proportion of subjects achieving a ≥ 4 -point reduction from baseline in DLQI at Week 16, the superiority of Apremilast 30 mg BID versus placebo will be tested. The hypotheses on superiority are defined as:

$$H_0: \pi_{APR} - \pi_{PBO} = 0$$

versus

$$H_1: \pi_{APR} - \pi_{PBO} > 0$$

Using an exploratory analysis on a subset of subjects meeting the following criteria: a) ScPGA ≥ 3 or b) NAPSI ≥ 1 or c) PPPGA ≥ 3 at baseline and DLQI ≥ 10 at baseline in the PSOR-008 and PSOR-009 Phase 3 studies, it was estimated that the proportion of subjects who achieved a ≥ 4 -point reduction from baseline in DLQI was 0.50 (97 responders out of 193 subjects) and 0.83 (337 responders out of 406 subjects) for placebo and Apremilast 30 mg BID, respectively.

Assuming a placebo DLQI responder proportion of 0.50 at Week 16, a minimum total sample size of 210 subjects (140 allocated to Apremilast 30 mg and 70 allocated to placebo) is needed to detect a 0.20 difference in the DLQI responder rate between Apremilast and placebo with at least 0.807 power using a two-sided test at the 0.05 level of significance. This sample size calculation is based on an unpooled variance, and determined using the commercial software EaST, Version 6.3. Allowing for an 24% discontinuation rate prior to Week 16, the sample size of 276 subjects should be sufficient.

5. GENERAL STATISTICAL CONSIDERATIONS**5.1. Reporting Conventions**

- The statistical test on the primary endpoint is at a 2-sided 0.05 significance level, any p-values reported for other endpoints are considered as summary statistics;
- P-values are rounded to 4 decimal places. P-values that round to 0.0000 are presented as '<0.0001' and p-values that round to 1.000 are presented as '>0.9999';
- Confidence intervals (CIs) are presented as 2-sided 95% CIs;
- Summary statistics consist of the number and percentage of subjects in each category for discrete variables, and the sample size, mean, median, Standard Deviation (STDEV), minimum, and maximum for continuous variables;
- All mean and median values are formatted to one more decimal place than the measured value, standard deviation values are formatted to two more decimal places than the measured value, minimum and maximum values are presented to the same number of decimal places as the measured value, and the 95% CI are formatted to two more decimal places than the measured value;

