- For continuous endpoints, the primary approach for handling missing data will be the multiple imputation (MI) method. Data will be analyzed using the analysis of covariance (ANCOVA) model with baseline values, treatment group and stratification factors (i.e., the manifestations of scalp psoriasis, nail psoriasis, palmoplantar psoriasis, genital psoriasis, or psoriasis in visible locations) as independent variables. SAS Proc Mixed will be used for the analysis. The least square mean (LS mean) with 95% CI for each treatment and difference of LS mean (Apremilast 30 mg BID - placebo) with 95% CI as well as the p-value will be provided.

Efficacy results will be considered statistically significant after consideration of the strategy for controlling the Type I error rate that is described in Section **Error! Reference source not found.** All statistical tests will be two-sided and be conducted at the 0.05 significance level, and p-values will be reported. For the efficacy endpoints evaluated after Week 16, only the treatment effect

Apremilast**Statistical Analysis Plan. Protocol CC-10004-PSOR-020****Amgen INC.**

estimates and the corresponding 95% confidence intervals (CIs) within each treatment arm will be provided to show the long-term treatment profile. No between group comparison will be conducted. Time plots on response rate or mean change (percent change) from baseline by treatment over the Placebo-controlled Phase and the Apremilast Extension Phase will be provided to show the maintenance of the treatment effect over time.

Data listings for quality of life assessments and efficacy assessments over the Placebo-controlled Phase and the Apremilast Extension Phase will be provided. An analysis phase flag will be included in each listing to indicate the phase that a record belongs to.

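### Week 32 and 52 response rates labelled ITT leave out everyone who did not enter the extension, and a maintenance plot joining them to all-randomised Week 16 rates can overstate durability.

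*SAP*

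**What the plan says.** Protocol 9.2 defines the ITT population as everyone randomised and adds: "This will be the primary population for the primary endpoint and all other quality of life and efficacy analyses". SAP 5.3.1 repeats the definition, and SAP 9.1 applies it to all efficacy evaluations. Protocol Table 2 and SAP 4.2.2 list the Week 32 and 52 endpoints without restricting them to a subset.

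SAP 9.4.2 then narrows the set: "The analyses will be conducted using the ITT population for subjects who entered the Apremilast Extension Phase". Binary endpoints use NRI and continuous endpoints use observed data. This leaves out two groups that SAP section 6 itself counts: those who discontinued in the placebo-controlled phase, and those who completed it but did not enter the extension.

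At Week 16, by contrast, SAP 9.3 uses the full ITT population, with MI as the primary rule and LOCF and NRI as supportive rules.

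SAP 9.1 also plans time plots by arm across both phases, which "will be provided to show the maintenance of the treatment effect over time". It does not say which analysis set or missing-data rule applies to the plotted points.

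SAP section 13 lists two departures from the protocol (multiplicity and the per-protocol definition). The entrants-only restriction is not among them.

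**The concern.** For subjects randomised to apremilast, Week 16 is not a new start. They are on one 52-week course, and the long-term effect at Weeks 32 and 52 is a stated secondary objective. Those who stop before Week 16 are unlikely to be a random subset. Protocol 11.1 lists adverse events and lack of efficacy among the reasons for stopping, and Protocol 6.5.5 notes that most reported severe gastrointestinal events came in the first few weeks of treatment. In the Week 32 and 52 tables these subjects do not count as non-responders; they are outside the denominator. NRI looks conservative there, but it acts only on losses after entry.

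Two things are at stake. A rate labelled ITT would be read as a share of all randomised subjects when it is not. And a curve that changes denominator at Week 16 could look flat, or rise, partly because early leavers were removed. No all-randomised Week 32 or 52 analysis of the secondary endpoints is planned that would show this.

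**Working it through.** **The plan's own figures.** SAP 4.4 plans for 210 evaluable subjects, "140 allocated to Apremilast 30 mg and 70 allocated to placebo", which it describes as "needed to detect a 0.20 difference in the DLQI responder rate between Apremilast and placebo with at least 0.807 power". For 0.50 against 0.70 at two-sided 0.05, the normal approximation gives 0.802 with unpooled variance and 0.807 with pooled variance. (The SAP says unpooled; the difference is small and does not bear on this point.) Allowing for discontinuation before Week 16:

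- SAP 4.4, 24%: 210/0.76 = 276.3, against 276 stated.
- Protocol 9.3, 18%: 210/0.82 = 256.1, against 255 stated.

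Both figures reproduce closely. At 2:1, 276 subjects give 184 on apremilast, and 184 x 0.76 is about 140 entrants.

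**Notation for the apremilast arm.** d is the share not entering the extension, p the Week 16 response rate among those who stay, e the later loss of response or dropout among entrants, and q the response rate that MI gives to early dropouts. The values of e and q and the 10% scenario for d are assumptions. So are that d is the same in both arms and that everyone who stays to Week 16 enters. The 70% for p is the SAP's planning rate (0.50 + 0.20).

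**Same visit, two denominators.**

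- Entrants-only NRI at Week 52 = p(1-e)
- All-randomised NRI at Week 52 = (1-d)p(1-e)
- Ratio = 1/(1-d), whatever p and e are

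The ratio is 1/0.76 = 1.32 at 24%, 1/0.82 = 1.22 at 18% and 1/0.90 = 1.11 at 10%. With p = 0.70, d = 24% and e = 0.15, the rates are 0.70 x 0.85 = 59.5% and 0.76 x 59.5% = 45.2%, a gap of 14.3 points. Over e = 0 to 0.30, the gap is 16.8 to 11.8 points at d = 24%, 12.6 to 8.8 at 18% and 7.0 to 4.9 at 10%. In counts, 84 responders are 60% of 140 entrants but 46% of 184 randomised.

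**Week 16 to Week 52 on a joined curve.** The Week 16 all-randomised rate is (1-d)p + dq, with q = 0 under NRI. With d = 24% and p = 0.70:

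| Week 16 point | Week 16 rate | Ratio if e = 0 (Week 52 = 70.0%) | Ratio if e = 0.15 (Week 52 = 59.5%) |
|---|---|---|---|
| NRI | 53.2% | 1.32 | 1.12 |
| MI, q = 0.40 | 62.8% | 1.11 | 0.95 |
| MI, q = 0.70 | 70.0% | 1.00 | 0.85 |
| Like for like among stayers | 70.0% | 1.00 | 0.85 |

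Against NRI, a curve with no real change rises by 16.8 points. Against MI with dropouts imputed 30 points worse than stayers, it rises by 7.2 points. Against MI with dropouts imputed like stayers, it does not rise.

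**Limit on the NRI row.** Under SAP 5.2.1 and 5.5, a discontinuation visit from Day 71 onward can supply a Week 16 value. The 53.2% assumes that no early leaver is an observed responder, so 16.8 points is an upper bound. The same mapping also creates a route that needs no imputation: an observed non-responder who stops at Day 90 lowers the Week 16 rate and then leaves the later denominator.

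**The case against.** A reader might infer that the SAP plots all-randomised Week 16 rates and entrants-only later rates on one curve, and so overstates maintenance by a known amount. The documents do not support that. SAP 9.1 names no denominator or imputation rule for the plot, so the joined curve is only the natural result of using the analyses that are planned. Nor is a same-visit gap, such as 60% of entrants against 46% to 49% of randomised (0.60 x 0.76 and 0.60 x 0.82), a measured bias in the trajectory. It compares two denominators, with an illustrative 60% and discontinuation rates that are sample-size allowances.

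Other points stand in part. For binary endpoints, the move from MI to NRI lowers the later points. The restriction is stated openly in 9.4.2, and Protocol 9.6.2 leaves estimation methods at Weeks 32 and 52 to the SAP. Early leavers are reported in the disposition tables as a share of those randomised, so a careful reader could rebuild the all-randomised NRI rate from the responder count. The extension results are descriptive, with no between-arm comparison, and lie outside the test hierarchy.

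These points limit the consequences but do not remove the problem. Protocol 9.6.2 delegates methods, whereas Protocol 9.2 fixes the population. A rate that readers must rebuild for themselves is not a reported ITT rate. The SAP's own section 9.6.2 summarises the manifestation endpoints at Weeks 16, 32 and 52 by NRI with no stated restriction to entrants, so a single rule across visits is already accepted there.

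**Conclusion.** The point holds as an inconsistency of population and label, with a conditional effect on the maintenance display. The Week 32 and 52 analyses are entrants-only under an ITT label, contrary to both documents' definition, and section 13 does not record the change.

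For the apremilast arm, the entrants-only NRI rate exceeds the all-randomised NRI rate at the same visit by a factor of exactly 1/(1-d). The size of d is not known: 1.22 to 1.32 rests on the planning allowances, and 1.11 on an assumed 10%. Whether the plot overstates maintenance depends on what is plotted at Week 16. It does if early leavers count there as non-responders; against the primary MI estimate the excess runs from zero upward.

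The point concerns only the arm randomised to apremilast. Placebo subjects start apremilast at Week 16, and for them entrants are a sensible set. The primary test is untouched.

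**What to change.** - For subjects randomised to apremilast, add Week 32 and 52 responder rates by NRI with all randomised subjects as the denominator, beside the entrants-only rates.
- Draw the maintenance plot for that arm with one denominator and one missing-data rule throughout, for example NRI in all randomised. The primary MI estimate at Week 16 stays in its own table. State the denominator and rule in the figure footnote.
- Label the points after Week 16 for subjects switched from placebo as entrants.
- Title the 9.4.2 tables as subjects who entered the extension, not ITT, and list the restriction in SAP section 13.

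The cost is one extra row per table, a relabelled figure and a line in section 13. Long-term figures for the apremilast arm will look less favourable, and an NRI curve will show a Week 16 value that differs from the primary MI result, which the footnote should explain.

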9.5. Subgroup Analysis

The consistency of the treatment effect on DLQI response at Week 16 will be assessed across the following subgroups:

- The randomization stratum based on the primary manifestation of plaque psoriasis: scalp psoriasis, nail psoriasis, palmoplantar psoriasis, genital psoriasis, and psoriasis in visible locations
- Sex (Male, Female)
- Race (White, Others)

Apremilast

Statistical Analysis Plan. Protocol CC-10004-PSOR-020

[figure not shown]
Amgen INC.

- Age category (< 65, \geq 65 years)
- Baseline BMI category (< 25, 25 to $<$ 30, \geq 30 kg/m²)
- Prior conventional systemic therapies (Yes/No)
- Prior biologic therapies (Yes/No)

Analysis will be based on ITT population and missing values will be imputed using MI method. The number (%) of subjects with improvement (\geq 4-point reduction) in DLQI and the between group difference will be summarized for each subgroup category. The adjusted treatment difference in proportion using the weighted average of the treatment differences across the strata (i.e., the 5 difficult to treat manifestation types) with the CMH weights, along with the associated 2-sided 95% CIs using a normal approximation to the weighted average will be provided within each subgroup. For subgroups based on primary manifestation, the adjusted estimates mentioned above are not applicable; unadjusted treatment differences in proportions and the associated 2-sided 95% CI using a normal approximation will be provided. Similarly, for other classification variables, if no subject falls into a stratum of the primary manifestation strata in a treatment group, unadjusted treatment differences in proportions and the associated 2-sided 95% CI using a normal approximation will be provided. Forest plot on rate difference and 95% CI by subgroups will be provided.

9.6. Analyses of Exploratory Efficacy Endpoints

For exploratory efficacy endpoints, descriptive summary statistics or proportion of subjects achieving pre-specified criteria will be summarized by treatment arm by time points.

9.6.2. Manifestation specific clinical endpoints at Week 16, Week 32, and Week 52

The following is the list of manifestation specific endpoints according to the pre-specified treatment improvement criteria.

- Achieving Static Physician Global Assessment (sPGA) score of 0 or 1 (among subjects randomized to the strata with moderate to severe psoriasis in visible areas, defined as sPGA \geq 3 at baseline, which include the dorsal hand, face, neck, or hairline) at Weeks 16, 32, 52
- Achieving Scalp Physician Global Assessment (ScPGA) score of 0 or 1 (among subjects randomized to the strata with moderate to severe scalp psoriasis, ScPGA \geq 3 at baseline) at Weeks 16, 32, 52

Apremilast

Statistical Analysis Plan. Protocol CC-10004-PSOR-020

Amgen INC.

- Achieving Nail Psoriasis Severity Index (NAPSI) score of 0 in the target fingernail (among subjects randomized to the strata with presence of nail psoriasis, defined as onycholysis and onychodystrophy in at least 2 fingernails at baseline) at Weeks 16, 32, 52
- Achieving Static Physician Global Assessment-Genitalia (sPGA-G) score of 0 or 1 (among subjects randomized to the strata with moderate to severe genital psoriasis, sPGA-G ≥ 3 at baseline) at Weeks 16, 32, 52
- Achieving Palmoplantar Psoriasis Physician Global Assessment (PPPGA) score of 0 or 1 (among subjects randomized to the strata with moderate to severe palmoplantar psoriasis, PPPGA ≥ 3 at baseline) at Weeks 16, 32, 52

The number and percentage of subjects with improvement among the subgroup of subjects demonstrating the corresponding manifestation at baseline by time point (including all visits with scheduled assessments and end of phase assessment) will be summarized based on data with NRI (including end of phase assessment). Shift tables for each of the manifestation assessment shift from baseline to post-baseline visits and end of phase assessment in all subjects will be provided based on DAO. The new onset on subject without such manifestations at baseline will also be assessed using shift tables.

Similar to the analysis mentioned above, all the manifestation specific endpoints will also be summarized based on subjects who met each specific condition regardless of whether they were stratified to the specific manifestation group.

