2. STUDY OBJECTIVES AND ENDPOINTS

Table 1: Study Objectives

Primary Objective
The primary objective of the study is to assess the impact of apremilast 30 mg twice daily (BID), compared to placebo, on health-related quality of life (qol) in subjects with manifestations of plaque psoriasis and impaired quality of life at Week 16.
Secondary Objective(s)
The secondary objectives are:

• To assess the efficacy and safety of apremilast 30 mg BID, compared to placebo in subjects with manifestations of plaque psoriasis and impaired quality of life at Week 16• To assess the long-term effects of apremilast 30 mg BID, with respect to quality of life, efficacy, and safety at Weeks 32 and 52
Exploratory Objective(s)
The exploratory objectives are:

• To assess the efficacy of apremilast 30 mg BID, compared to placebo in subgroups of subjects with specific manifestations [REDACTED]

Table 2: Study Endpoints

Endpoint	Name	Description	Timeframe
Primary	Dermatology Life Quality Index (DLQI)	Proportion of subjects who achieve a \geq 4-point reduction from baseline	Weeks 16
Secondary	DLQI	Proportion of subjects who achieve a \geq 4-point reduction from baseline	Weeks 32, 52
	DLQI	Mean change from baseline	Weeks 16, 32, 52
	Itch Numeric Rating Scale (NRS)	Mean change from baseline in Itch NRS score	Weeks 16, 32, 52
	Skin Discomfort/Pain Visual Analog Scale (VAS)	Mean change from baseline in skin discomfort/pain VAS	Weeks 16, 32, 52
	Body Surface Area (BSA)	Mean percent change in BSA affected by psoriasis	Weeks 16, 32, 52
	Patient Benefit Index (PBI)	Proportion of subjects who achieve PBI score of ≥ 1	Weeks 16, 32, 52
	Psoriasis Area Severity Index (PASI)	Proportion of subjects who achieve PASI < 3	Weeks 16, 32, 52

Table 2: Study Endpoints (Continued)

Endpoint	Name	Description	Timeframe
	European Quality of Life 5-Dimension (EQ-5D)	Mean percent change from baseline in EQ-5D score	Weeks 16, 52
	Work Productivity and Activity Impairment Questionnaire: Psoriasis (WPAI: PSO)	Mean change in WPAI domain scores	Weeks 16, 52
	Treatment-emergent Adverse events	Frequency and incidence rate of any TEAE by SOC, PT, severity, and relationship of adverse events (AEs) to investigational product (IP).	During double-blinded treatment and throughout the duration of the apremilast treatment

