9.6.2. Secondary and Exploratory Efficacy Endpoints

For continuous endpoints at Week 16, an analysis of covariance (ANCOVA) model with treatment and randomization strata as fixed effects and corresponding baseline value as a continuous covariate will be employed. Missing data will be addressed using multiple imputation. The adjusted means and standard errors will be reported for each of the treatment group using the ANCOVA model, as well as the estimated treatment effect (ie, difference in the adjusted treatment means, their standard errors, and 95% confidence intervals). In addition, descriptive statistics will be provided based upon the observed data which will not address missing data. Details regarding the methods of estimation to be performed at Weeks 32 and 52 will be provided in the statistical analysis plan (SAP).

[figure not shown]
For discrete endpoints, the CMH estimation method stratified by the randomization strata for assessing the difference in proportion between the treatment groups will be conducted. The weights in the CMH estimation method will be same as those used in the primary endpoint analysis. The adjusted difference in the proportions between the treatment groups, their standard errors, and corresponding 95% confidence intervals will be reported. Missing data will be addressed through multiple imputation similar to that of the primary endpoint analysis. In addition, descriptive statistics involving the sample size, the number of responders, and proportion of responders will be summarized by treatment group. Details regarding the methods of estimation to be performed at Weeks 32 and 52 will be provided in the SAP.

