3.3. Exploratory Objectives

The exploratory objectives are:

- To assess the efficacy of Apremilast compared to placebo in subgroups of patients with specific manifestations

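### For the five manifestation-specific clinical endpoints, the SAP drops the Week 16 treatment difference and 95% CI that the protocol prescribes, and moves from multiple to non-responder imputation, without declaring either change

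*SAP*

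**What the plan says.** The exploratory objective is comparative in both documents. Protocol Table 1 has "To assess the efficacy of apremilast 30 mg BID, compared to placebo in subgroups of subjects with specific manifestations"; SAP 3.3 has "To assess the efficacy of Apremilast compared to placebo in subgroups of patients with specific manifestations".

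The protocol section that sets the method is headed "9.6.2. Secondary and Exploratory Efficacy Endpoints". It says: "For discrete endpoints, the CMH estimation method stratified by the randomization strata for assessing the difference in proportion between the treatment groups will be conducted". That section also fixes the output: "The adjusted difference in the proportions between the treatment groups, their standard errors, and corresponding 95% confidence intervals will be reported". On missing data: "Missing data will be addressed through multiple imputation similar to that of the primary endpoint analysis". Only the methods for Weeks 32 and 52 are left to the SAP.

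SAP 9.6 says: "For exploratory efficacy endpoints, descriptive summary statistics or proportion of subjects achieving pre-specified criteria will be summarized by treatment arm by time points". SAP 9.6.2 then plans the number and percentage of responders on NRI data, with shift tables on observed data, for the five manifestation endpoints. It adds that these endpoints "will also be summarized based on subjects who met each specific condition regardless of whether they were stratified to the specific manifestation group". No difference or interval for a difference is planned in either set.

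**The concern.** The five endpoints measure clearance or near-clearance of the disease that placed the subject in a stratum. Randomisation is by permuted blocks within manifestation (SAP 4.3), so the Week 16 contrast inside each stratum is a randomised comparison. It is also the last one available, because everyone receives apremilast from Week 16.

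The protocol asks for that contrast to be estimated. The SAP reports its two halves side by side, without the estimate or its uncertainty, and does not record the change. The protocol's amendment justification says that equal block-randomisation across manifestations was removed because enrolment rates differed, so some strata may be small. Week 16 results may also be published before the study ends. Bare percentages from small 2:1 strata are easy to over-read.

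**Working it through.** **Text comparison (Week 16, five manifestation endpoints)**

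| Item | Protocol 9.6.2 | SAP 9.6 and 9.6.2 | Listed in SAP 13? |
|---|---|---|---|
| Estimate | Difference in proportions, CMH, stratified | None; number and percentage by arm | No |
| Precision | SE and 95% CI of the difference | None stated | No |
| Missing data | Multiple imputation | NRI | No |

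Three places could have closed the gap.
- SAP 9.1 restricts its CMH analysis to the primary and secondary endpoints.
- SAP 9.5 gives an unadjusted difference and 95% CI in each manifestation stratum, but only for DLQI response.
- SAP 13 lists two departures from the protocol: multiplicity and the per-protocol population.

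Some exploratory text in SAP 9.6 is redacted. The manifestation text in 9.6.2 is intact and states its own method, so redaction does not explain the omission.

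Each endpoint is first defined within one randomisation stratum. There the stratified CMH estimate reduces to a simple risk difference. Stratification matters again for the wider set of all subjects meeting the condition, which crosses strata.

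**Size of the intervals**

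The plan gives no precision figure for these endpoints to reproduce. The inputs are N = 276 and 2:1 allocation (SAP 4.1). Stratum sizes and response rates are assumed.

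Half-width = 1.96 × √[pA(1 − pA)/nA + pP(1 − pP)/nP], with pA = 0.40 and pP = 0.20:

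- Equal fifths, 276/5 ≈ 55 (37 vs 18): 1.96 × √(0.24/37 + 0.16/18) = 1.96 × √0.01538 = 0.243
- Stratum of 30 (20 vs 10): 1.96 × √(0.24/20 + 0.16/10) = 1.96 × √0.0280 = 0.328
- Stratum of 80 (53 vs 27): 1.96 × √(0.24/53 + 0.16/27) = 1.96 × √0.01045 = 0.200

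Keeping a true difference of 0.20, but varying the placebo rate from 0.10 to 0.50 and the stratum from 100 down to 30, the half-width runs from about 0.15 to 0.37.

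**Which interval**

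SAP 9.5 uses a normal approximation. Exact coverage of a nominal 95% interval, found by summing binomial probabilities over all outcomes for 20 vs 10:

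| True rates (apremilast vs placebo) | Wald | Newcombe score |
|---|---|---|
| 0.40 vs 0.20 | 92.1% | 94.7% |
| 0.10 vs 0.05 | 88.7% | 98.6% |

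In the second row the chance of no placebo responders is 0.95^10 = 0.60. If both arms have none, the Wald interval has zero width. A score-based interval avoids this.

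**The case against.** The strongest reply has four parts.

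1. *The objective is not abandoned.* It names no endpoint, and SAP 9.5 serves it for DLQI response, the trial's primary measure, with a difference, a CI and a forest plot by manifestation. This stands. A reader might infer that the SAP leaves the comparative objective unanswered altogether; SAP 9.5 shows that it does not. The gap is confined to the clinical endpoints.

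2. *The information is still there.* Under NRI there are no missing outcomes, and SAP 5.1 requires sample sizes in every summary table, so a reader can compute the within-stratum difference and its CI. This also stands, and it would be too strong to say that precision is lost. It does not reach the wider set: the planned counts there are not said to be split by stratum, so a stratified difference could not be rebuilt from them. SAP 5.1 also gives a display format for 95% CIs alongside percentages, but that does not commit 9.6.2 to one.

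3. *Exploratory endpoints may be descriptive.* In general, yes. Here the protocol section names exploratory endpoints and prescribes estimation for them. A reader might infer that a confirmatory test has been dropped. It has not: Protocol 9.6 treats every p-value other than the primary one as a summary statistic, so what is missing is estimation.

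4. *The strata are too small.* SAP 9.5 already plans differences with CIs in the same strata. Small strata are a reason to choose a better interval and to show it.

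**Conclusion.** The point holds as an undeclared departure from the protocol, limited to Week 16 and to five exploratory clinical endpoints. The difference and its 95% CI are dropped, and multiple imputation becomes NRI; SAP 13 mentions neither.

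The consequence is modest. The primary analysis, the sample size and the test hierarchy are untouched. Weeks 32 and 52 are not part of the contradiction, because the protocol defers those methods to the SAP and all subjects are by then on apremilast.

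The interval widths of about ±20 to ±33 points illustrate why precision should be shown. They rest on assumed strata of 80 to 30 subjects and assumed rates of 0.40 and 0.20. Neither is in the documents, so the widths are not predictions for this trial.

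**What to change.** In SAP 9.6.2, for Week 16 only:

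- For each endpoint within its randomised stratum, add the apremilast minus placebo difference in proportions on the planned NRI data, with a score-based 95% CI (Newcombe or Miettinen–Nurminen), because strata may be small and rates near zero.
- For all subjects meeting the condition at baseline, whatever their stratum, add the CMH-weighted difference stratified by manifestation, with 95% CI. Carry over SAP 9.5's fallback to an unadjusted difference when a stratum has no subject in one arm, again with a score-based CI.
- Report no p-values, and leave Weeks 32 and 52 descriptive.

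In SAP 13, list NRI in place of multiple imputation for these endpoints.

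If the sponsor prefers to keep the summaries purely descriptive, SAP 13 should at least say so and give the reason. That would make the departure transparent but would still leave the objective unanswered for these endpoints.

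The cost is a few lines of SAP text and one column in tables already planned. No new data are needed. Priority is low.
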